Aim 3: To compare postoperative rates of surgical site infection (SSI) in women who receive chlorhexidine gluconate versus povidone iodine vaginal antiseptic preparation preoperatively, defined as per CDC guidelines (described below). **Hypothesis:** Chlorhexidine gluconate will demonstrate a non-inferior rate of postoperative SSI compared to povidone iodine.

Aim 4: evaluate vaginal and vulvar irritation for post groups on postop day 1 as measured by a 5-point vaginal irritation scale previously used in a safety and tolerability study examining vaginal chlorhexidine gluconate (Al Niaimi et al) **Hypothesis:** Chlorhexidine gluconate will demonstrate a non-inferior rate of postoperative vaginal and vulvar irritation for postop day 1.

2. Background

Steady improvements have been made in surgical infection control over the past century including improved instrument sterilization methods, operating room ventilation, surgical barriers including gowns and drapes, surgical technique, preoperative antimicrobial prophylaxis, and preoperative cleaning or prepping of the surgical site. Despite these advancements, UTIs and SSIs continue to be a common cause of postoperative morbidity.

Urinary Tract Infections are one of the most common post-operative complications associated with urogynecologic surgery. One study estimated that 33% of women develop UTIs in the 12 week period following surgical treatment for stress urinary incontinence (Anger et al). UTIs are associated with increased health care costs, antibiotic resistance, and morbidity and mortality for patients. Because UTIs are so common, they are used as a quality metric and tracked by the Joint Commission, the Centers for Medicare and Medicaid Services (CMS), and National Surgical Quality Improvement Program (NSQIP), among others.

Another concern following pelvic surgery (which may include a vaginal approach or surgery on the vagina) is development of surgical site infections (SSI). A recent study found that SSIs were among the most common healthcare-associated infection, accounting for 31% of all healthcare-associated infections (HAI) among hospitalized patients. (Magill 1) Vaginal surgery is classified as clean-contaminated procedures because of the natural bacterial flora of the vagina. This generally increases infection risk over clean procedures.

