We will perform a single masked, non-inferiority randomized-controlled trial to compare the effectiveness of chlorhexidine gluconate and povidone iodine pre-surgical vaginal antiseptic cleaning preparations prior to pelvic surgery (which may include a vaginal approach or surgery on the vagina). The target population are those patients presenting for urogynecologic surgery in the University of New Mexico health system. Participants will be masked as they will not be informed regarding which intervention they receive while under anesthesia at the start of their scheduled procedure. All women will give written or verbal consent prior to enrollment. It is not feasible to mask the surgeon, as the two antiseptic preparations are colored differently which is evident throughout surgery.

4. Inclusion and Exclusion Criteria

We will recruit patients who present to the University of New Mexico (UNM Women's Care Eubank Clinic or Sandoval Regional Medical Center) with urogynecologic conditions requiring pelvic surgery (which may include a vaginal approach or surgery on the vagina). Patients will receive usual care including evaluation of prior medical history and physical exam, any necessary diagnostic studies and preoperative workup. All patients will be offered typical treatment options regardless of their desire to participate in the research study.

Patients will be enrolled if they meet the inclusion and do not meet the exclusion criteria.

The inclusion criteria are:

- Female Subjects >18 years of age
- English or Spanish speaking/reading
- Must be able to provide informed consent.
- Undergoing urogynecologic procedures or surgery at UNM, OSIS, or SRMC

Exclusion criteria:

- Pregnant - all patients are verified regarding pregnancy status prior to gynecologic surgical intervention at all sites of surgery within the UNM system –

for patients who are premenopausal and have a uterus, a urine pregnancy test is administered in the preoperative setting. Pregnancy status is also determined prior to this in the office setting by interview and patient provided history prior to offering surgery to the patient.

- Inability to return for follow-up visits
- No concurrent need for vaginal antiseptics, such as cases of sacral neuromodulation
- Lack of telephone
- Known allergy to either antiseptic agent
- Prisoners will not be eligible to participate in this study

5. Number of Subjects

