This single masked, non-inferiority randomized controlled trial will be conducted at the UNM Eubank Clinic and SRMC Urogynecology clinic and associated operating rooms. We will recruit at least 200 participants between the sites. All collaborating investigators are members of the Urogynecology division at UNM.

The primary aim of our study is to determine if UTI rates are similar between typical preoperative vaginal antiseptic cleaning solutions (i.e. chlorhexidine gluconate vs. povidone iodine). The target population will be patients with urogynecologic conditions desiring surgical management that would require vaginal surgical preparation. If a patient decides during their clinic visit to proceed with surgical management that would require vaginal surgical preparation they will be considered for the study. If the patient is interested in surgical management and fulfills study inclusion criteria, we will then offer her the choice of participating in this study. Written or verbal consent will be obtained from all participants by research staff prior to enrollment. All participants will then complete baseline surveys including patient demographics, medical/surgical history, and contact information, which are attached as supporting documents. This information will be collected from the patient on the day of enrollment with information supplemented from their medical record as needed.

Randomization assignment will be generated by a computer based randomization table and assigned by a research coordinator. Assignments will be kept in sealed opaque envelopes

numbered sequentially. On the day of the patient’s surgery, after previously signing or verbalizing consent and deciding to participate, the next envelope in the sequence will be opened, randomizing the patient to chlorhexidine gluconate or povidone iodine. The therapy allocation will then be carried out.

Patients randomized to chlorhexidine gluconate or povidone iodine will undergo standardized preoperative surgical site preparation by surgical staff. Abdominal cleaning will be done with chlorhexidine gluconate in 70% isopropyl alcohol as this is the standard antiseptic used throughout the institution. Vaginal antiseptic cleaning will be performed with either chlorhexidine or povidone based on the randomization scheme, this will be performed in a standardized fashion as described in supplemental vaginal preparation instruction document (included in appendix A).

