If a patient demonstrates an allergic reaction to either antiseptic (povidone iodine or chlorhexidine gluconate), they will be routinely treated for allergic symptoms and informed of the antiseptic type, the allergy will also be added to their medical record.

Table 1: Outcomes collected at various time points

	Baseline	2 weeks	6 weeks
Demographic and medical history	X		
Follow up questionnaire	X	X	X
Vaginal irritation questionnaire	Postop day 1		

Our primary outcome is to report the rates of postoperative urinary tract infections for each cohort at 2 weeks postoperatively. It is our standard of care to see patients back at 2 weeks and 6 weeks following surgical management of urogynecological conditions.

If patients are unable to follow up in clinic as standard care, telephone communication may be used to ask patients if they have received care at an outside facility for urinary tract infection or other infection related to surgical treatment.

Outcome Measures:

- Urinary tract infection (UTI): Patients with >100k colony forming units on urine culture, symptomatic patients with >10k colony forming units on urine culture or reported UTI symptoms resulting in empiric treatment without urine culture.**
- Surgical Site Infection (SSI): Surgical site infection as defined by the below criteria in the 6 week postoperative period.**

- 1) We will categorize SSI based on CDC criteria (ref) adapted from the CDC guidelines as referenced below. We will record SSI events 6 weeks after surgery.
 - a. CDC Criterion: Surgical Site Infection (SSI)
 - i. Superficial incisional SSI must meet the following criteria:
 1. Date of event for infection occurs within 6 weeks after any operative procedure (where day 0 is the procedure date)
 2. AND involves only skin and subcutaneous tissue of the incision
 3. AND patient has at least one of the following:
 - a. Purulent drainage from the superficial incision.
 - b. Organisms identified from an aseptically-obtained specimen from the superficial incision or subcutaneous tissue by a culture or non-culture based microbiologic testing method which is performed for purposes of clinical diagnosis or treatment (for example, not Active Surveillance Culture/Testing (ASC/AST).

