 - c. Superficial incision that is deliberately opened by a surgeon, attending physician** or other designee and culture or non-culture based testing is not performed. AND patient has at least one of the following signs or symptoms: pain or tenderness; localized swelling; erythema; or heat.
 - d. Diagnosis of a superficial incisional SSI by the surgeon or attending physician** or other designee.
 4. ** The term attending physician for the purposes of application of the SSI criteria may be interpreted to mean the surgeon(s), infectious disease, other physician on the case, emergency physician or physician's designee (nurse practitioner or physician's assistant or nurse midwife).
 5. There are two specific types of superficial incisional SSIs:
 6. Superficial Incisional Primary (SIP) - a superficial incisional SSI that is identified in the primary incision in a patient that has had an operation with one or more incisions (for example, C-section incision or chest incision for CBGB)
 7. Superficial Incisional Secondary (SIS) - a superficial incisional SSI that is identified in the secondary incision in a patient that has had an operation with more than one incision (for example, donor site incision for CBGB)
 8. The following do not qualify as criteria for meeting the definition of superficial SSI:

9. Diagnosis/treatment of cellulitis (redness/warmth/swelling), by itself, does not meet criterion "d" for superficial incisional SSI. Conversely, an incision that is draining or that has organisms identified by culture or non-culture based testing is not considered a cellulitis.
10. A stitch abscess alone (minimal inflammation and discharge confined to the points of suture penetration).
11. A localized stab wound or pin site infection- Such an infection might be considered either a skin (SKIN) or soft tissue (ST) infection, depending on its depth, but not an SSI
Note: A laparoscopic trocar site for an operative procedure is not considered a stab wound.

ii. Procedure-associated Module SSI Deep incisional SSI Must meet the following criteria:

1. The date of event for infection occurs within 6 weeks after the operative procedure (where day 0 = the procedure date) according to the list in Table 2
2. AND involves deep soft tissues of the incision (for example, fascial and muscle layers)
3. AND patient has at least one of the following:
 - a. Purulent drainage from the deep incision.

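### Aim 3 attributes surgical site infection to the vaginal preparation, but its definition also counts abdominal and trocar-site infections, where both arms receive the same antiseptic

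*Combined protocol and SAP*

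**What the plan says.** Section 1, Aim 3, compares SSI rates in "women who receive chlorhexidine gluconate versus povidone iodine vaginal antiseptic preparation preoperatively". Its hypothesis is that "Chlorhexidine gluconate will demonstrate a non-inferior rate of postoperative SSI compared to povidone iodine".

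Section 12 (Study Procedures) limits the randomised difference to the vagina: "Vaginal antiseptic cleaning will be performed with either chlorhexidine or povidone based on the randomization scheme". The abdomen is handled the same way in both arms: "Abdominal cleaning will be done with chlorhexidine gluconate in 70% isopropyl alcohol as this is the standard antiseptic used throughout the institution".

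The SSI criteria under Outcome Measures in Section 12 cover superficial, deep and organ/space infection within 6 weeks. They split incisional events by depth and into primary and secondary incisions. One superficial type is "a superficial incisional SSI that is identified in the secondary incision" of an operation with more than one incision, and the deep criteria have a matching type. Under the stab-wound exclusion the protocol adds: "Note: A laparoscopic trocar site for an operative procedure is not considered a stab wound". Trocar-site infections are therefore not removed by that exclusion.

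Nowhere do the criteria class an event as vaginal or abdominal. Section 13 (Data Analysis) gives no SSI margin, effect scale, expected rate, site-specific analysis or allowance for surgical approach. Sections 1, 3 and 4 describe the surgery as pelvic, with a vaginal approach possible but not required.

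**The concern.** Aim 3 asks what the vaginal preparation does to SSI. A woman in the povidone iodine arm whose trocar site becomes infected is an Aim 3 event charged to povidone iodine, although that skin was prepared with chlorhexidine-alcohol. The same infection in the chlorhexidine arm is charged to chlorhexidine. Such events are expected equally often in both arms and say nothing about the agent under test. The background in Section 2 itself links SSI after abdominal surgery to the agent used for abdominal antisepsis, and here that agent does not differ between arms.

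At stake is what an Aim 3 result can be taken to mean. A finding of non-inferior SSI, or a failure to show it, could partly reflect how many abdominal infections were mixed in.

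**Working it through.** **Inputs from the plan.** 58 per group is the evaluable target and 100 per group the enrolment ceiling (Section 5). Alpha is 0.05, sidedness not stated. The only margin anywhere is an absolute 10% for urinary tract infection (Section 5). There is no SSI figure to reproduce, because the plan gives no SSI rate, margin or sample size.

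**Assumptions.** Vaginal-site SSI (v) is 2% on povidone iodine and 4% on chlorhexidine, a true doubling. Abdominal-site SSI (a) is 0% to 4% and equal in both arms. Tests are one-sided at 0.05 with a normal approximation. Margins are either a ratio of 2 or a difference of 10 points; neither is stated for SSI.

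**Formulas.**
- All-site rate per arm: p = 1 − (1 − v)(1 − a). For a = 1%: 1 − 0.98 × 0.99 = 2.98% and 1 − 0.96 × 0.99 = 4.96%.
- Difference: d = (0.04 − 0.02)(1 − a). For a = 1%: 0.02 × 0.99 = 1.98 points.
- SE of the difference: √[p₁(1 − p₁)/n + p₂(1 − p₂)/n].
- Chance of declaring non-inferiority on the difference: Φ[(0.10 − d)/SE − 1.645]. For a = 1%, n = 58: Φ[(0.10 − 0.0198)/0.0362 − 1.645] = 71.6%.
- Chance on the ratio: Φ[(ln 2 − ln RR)/SE(ln RR) − 1.645], where SE(ln RR) = √[(1 − p₁)/(n p₁) + (1 − p₂)/(n p₂)].

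| a | Rates (PI / CHG) | Ratio | Difference (points) | SE, n=58 (points) | Ratio margin 2: n=58 / n=100 | 10-point margin: n=58 / n=100 |
|---|---|---|---|---|---|---|
| 0% | 2.00% / 4.00% | 2.00 | 2.00 | 3.16 | 5.0% / 5.0% | 81.2% / 95.3% |
| 1% | 2.98% / 4.96% | 1.66 | 1.98 | 3.62 | 7.3% / 8.2% | 71.6% / 89.7% |
| 2% | 3.96% / 5.92% | 1.49 | 1.96 | 4.02 | 9.8% / 11.8% | 63.9% / 83.7% |
| 4% | 5.92% / 7.84% | 1.32 | 1.92 | 4.70 | 14.7% / 19.5% | 53.0% / 73.0% |

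The last two columns give the chance of declaring non-inferiority. In the ratio column the true vaginal-site ratio equals the margin, so every such declaration is false with respect to the vaginal site.

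**Second scenario, 4% versus 8%.** For a = 1% to 4%, the ratio falls from 2.00 to 1.80–1.49 and the difference from 4.00 to 3.96–3.84 points. At 58 per arm the chance of meeting a 10-point margin falls from 39.0% to 35.9%–30.0%.

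**Simple form of the ratio.** If a fraction f of povidone iodine SSIs are abdominal and the rest double, the observed ratio is f + 2(1 − f) = 2 − f. This gives 1.95 at f = 5%, 1.90 at 10%, 1.75 at 25%, 1.50 at 50% and 1.25 at 75%.

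**Reading.** On the ratio scale the added events favour non-inferiority. On the difference scale they cost precision and make non-inferiority harder to show when the true difference lies inside the margin. When it lies outside, little changes: with 4% versus 12% and an assumed 5-point margin, the chance at 58 per arm goes only from 1.2% to 1.8% at a = 4%. The approximation is crude with so few events: 58 × 0.0200 = 1.2 and 58 × 0.0784 = 4.5 per arm at the extremes of the table.

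**The case against.** All-site SSI in all randomised women answers a legitimate pragmatic question: total surgical infection under each preparation policy. Uniform abdominal preparation removes a co-intervention difference, and the randomised comparison remains valid. This stands, and it is why all-site SSI should be kept. It does not make the endpoint specific to the vaginal preparation that Aim 3 names. Organ/space infection may also respond to the vaginal agent once the vagina has been opened, so the clear problem is confined to abdominal incisional and trocar-site events.

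Three stronger readings are tempting but not supported.

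- A reader might infer that the mixing biases Aim 3 toward non-inferiority in general. That needs a ratio margin. The plan states no SSI scale, its only margin is absolute, and on that scale the main effect is lost precision.
- A reader might infer from the inclusion criterion "Undergoing urogynecologic procedures or surgery at UNM, OSIS, or SRMC" that many women without any vaginal incision dilute the denominator. This would shrink even an absolute difference: if half had none of the relevant infections, 4% versus 8% would become 2% versus 4%. But Section 4 excludes women with no need for vaginal antiseptics, Section 12 targets surgery that requires vaginal preparation, and Section 18 describes enrolled women as having agreed to prolapse surgery. None of these strictly requires a vaginal incision, but together they narrow the group, and its size is unknown.
- A reader might take "Date of event for infection occurs within 6 weeks after any operative procedure" as extending the endpoint to any anatomical site. It is a timing criterion. The breadth comes from the incision types and the trocar note.

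The follow-up questionnaire is not in the text available, so it may already capture site. The criteria and the analysis section do not call for it.

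**Conclusion.** The concern holds as a mismatch between Aim 3 and its endpoint: the endpoint includes infections that the randomised agent cannot plausibly affect, and the plan does not provide for separating them. The consequence depends on a scale the plan does not state. Under the assumed rates of 2% and 4% with 1% to 4% abdominal SSI, a true ratio of 2.00 would appear as 1.66 to 1.32. On the difference scale, the chance of meeting an assumed 10-point margin at 58 per arm would fall from 81% to between 72% and 53%.

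These figures show direction and plausible range and do not estimate this trial. They rest on assumed SSI rates, an assumed doubling, assumed margins and equal abdominal rates in both arms. The share of women with abdominal incisions is not given; if few have them, the effect is small. Aim 3 is secondary, and the primary urinary tract infection comparison is unaffected. The change is still worth making because it is cheap and site is hard to reconstruct later.

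**What to change.** In Section 12, record the anatomical site of each SSI: vaginal or perineal incision, abdominal or trocar incision, or pelvic organ/space. Ask the same at telephone follow-up, where Section 12 allows infections treated elsewhere to be reported.

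For Aim 3, pre-specify a comparison, in all randomised women, of SSI of a vaginal or perineal incision or of the pelvic organ/space, and state its effect scale and margin. Keep all-site SSI by the adapted CDC criteria alongside it, and report abdominal and trocar-site SSI separately by arm. Restricting the denominator to women whose planned procedure includes a vaginal or perineal incision, fixed before the envelope is opened, is at most an optional sensitivity analysis.

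The cost is one field on the follow-up form and wording in Aim 3, Section 12 and Section 13, with no extra visits, staff or patients. The downside is fewer events in the site-specific comparison, in an endpoint that may already have only a handful per arm.

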20. Recruitment Methods	18
21. Provisions to Protect the Privacy Interests of Subjects	19
22. Economic Burden to Subjects	19
23. Compensation	19
24. Compensation for Research-Related Injury	19
25. Consent Process	20
26. Documentation of Consent	21
27. Study Test Results/Incidental Findings	21
28. Sharing Study Progress or Results with Subjects	22
29. Inclusion of Vulnerable Populations	22
30. Community-Based Participatory Research	22
31. Research Involving American Indian/Native Populations	22
32. Transnational Research	22
33. Drugs or Devices	22
34. Principal Investigator's Assurance	23

1. Objectives

The primary objective of this research study is to perform a single-blinded, non-inferiority randomized-controlled trial to compare the effectiveness of two pre-surgical vaginal antiseptic cleaning solutions prior to pelvic surgery (which may include a vaginal approach or surgery on the vagina). Our central hypothesis is that chlorhexidine gluconate will be non-inferior to povidone iodine and that both antiseptic solutions will equally prevent postoperative infections. The specific aims are:

Aim 1: To compare postoperative urinary tract infection (UTI) rates between women cleaned with chlorhexidine gluconate (CHG) versus povidone iodine (PI) preoperatively. For the purposes of this study, UTI will be defined as: 1) greater than 100,000 CFUs on culture, or 2) at least 10,000 colony forming units on urine culture, in a symptomatic patient, or 3) patient reported UTI symptoms empirically treated within 2 weeks after surgery. Our primary **hypothesis** is that chlorhexidine gluconate will be non-inferior to povidone iodine with respect to the number of UTIs identified and treated within 2 weeks of surgery.

Aim 2: To compare postoperative culture proven urinary tract infection (UTI) rates between women cleaned with chlorhexidine gluconate (CHG) versus povidone iodine (PI) preoperatively. For the purposes of this aim UTI will be defined as: 1) greater than 100,000 CFUs on culture, or 2) at least 10,000 colony forming units on urine culture, in a symptomatic patient. Our primary **hypothesis** is that chlorhexidine gluconate will be non-inferior to povidone iodine with respect to the number of UTIs identified and treated within 2 weeks of surgery.

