The primary outcome of this study is to determine rates of urinary tract infections in the period 2 weeks post-surgery for both cohorts. For the purposes of this study, UTI has been defined in section 1 (objectives), aim 1. We have powered the study based on a 10% difference in UTI rates between groups within 2 weeks of surgery. Based on a non-inferiority study design and a between group difference of less than or equal to 10%, we need 58 patients per group (chlorhexidine gluconate versus povidone iodine) to detect no difference with an alpha =0.05 and with 80% power. Assuming a high dropout rate of 20%, we will enroll a total of up to 200 patients (100/group), or until we reach our primary endpoint of 2 week follow up for 116 patients, or 58 patients in each group. We have increased the numbers due to COVID-19 and loss to follow-up.

This is not a multi-center study. Data will be housed at the Eubank clinic.

6. Study Timelines

Timeline	May 2019- April 2020	May 2020-Sept 2020
Subject recruitment, therapy, through 3 month follow up	x	x
Data analysis		x
Manuscript preparation		x

Over the past 12 months, 318 urogynecology cases were performed at UNM and SRMC. Assuming a conservative estimate of 50% enrollment, recruitment of up to 200 patients would be feasible over the next 3 month period.. Since subjects will be followed for 6 weeks after surgery, it may take up to 14 months to collect 6 weeks of follow up data. We estimate that data analysis, manuscript preparation and publication will take an additional 10 months.

7. Study Endpoints

The **primary endpoint** of our study is to determine the incidence of urinary tract infections within weeks of surgery in women who undergo pelvic surgery (which may include a vaginal approach or surgery on the vagina) with either chlorhexidine gluconate or povidone iodine vaginal antiseptic preparation. Our **secondary endpoints** are to investigate SSI rates in the two groups at 6 weeks, and vaginal irritation on the first postoperative day.

Given the extremely low-risk nature of the therapeutic interventions, we do not have any **safety endpoints**. However, any patients noted to have an allergic response will be treated according to the normal standard of care depending on the severity of their allergic reaction.

8. Research Setting

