 - c. an abscess or other evidence of infection involving the organ/space that is detected on gross anatomical or histopathologic exam, or imaging test evidence suggestive of infection. AND meets at least one criterion for a specific organ/space infection site.

13. Data Analysis

Data Analysis: Between and within group differences will be evaluated using Wilcoxon-Mann-Whitney test for categorical variables and t-tests for continuous variables. If there are any baseline differences between groups, a multivariate analysis will determine the contribution of these differences to observed differences (if any) between groups.

Power Analysis: Power analysis was performed based on previously reported rates of postoperative urinary tract infection after urogynecologic surgery as well as rates of relative reduction in infection with chlorhexidine presurgical preparations as opposed to povidone iodine. To achieve significance for a non-inferiority study using these assumptions we would need 116 patients, 58 per group to detect this difference with $\alpha = 0.05$ and with 80% power.

To allow for a dropout or loss to follow up of 20% due to the pandemic, we will enroll at least 200 patients.

Comparative Cost Analysis

The cost analysis will be conducted from patient and health system perspective and will be expressed as incremental cost required to prevent one episode of UTI.

Direct and indirect cost of health care utilization will be obtained when episodes of UTI occur, including the patient reported travel expenses and copays to obtain care, cost of UTI diagnosis with urine dipstick, urinalysis, and urine culture standardized to University of New Mexico Health Sciences Center institutional pricing as well as the cost of antibiotics for treatment.

14. Provisions to Monitor the Data to Ensure the Safety of Subjects

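### The primary hypothesis is non-inferiority on 2-week UTI, but the planned tests are tests of no difference, with no interval, sidedness or decision rule tied to the 10%

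*Combined protocol and SAP*

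**What the plan says.** Sections 1, 2, 3 and 12 all describe a non-inferiority trial. The Aim 1 hypothesis in Section 1 is that "chlorhexidine gluconate will be non-inferior to povidone iodine with respect to the number of UTIs identified and treated within 2 weeks of surgery". The central hypothesis in the same section adds that "both antiseptic solutions will equally prevent postoperative infections".

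Section 5 justifies 58 per group as follows: "Based on a non-inferiority study design and a between group difference of less than or equal to 10" percent, "to detect no difference with an alpha =0.05 and with 80% power". The 10% is not called a margin, is not said to be absolute, and is not used again.

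Section 13 gives the analysis in one sentence: "Between and within group differences will be evaluated using Wilcoxon-Mann-Whitney test for categorical variables and t-tests for continuous variables". The rest of that section is a multivariate analysis if baseline differences appear, a power statement and a cost analysis. The power statement says "To achieve significance for a non-inferiority study using these assumptions we would need 116 patients" and refers to unnamed UTI rates and to "rates of relative reduction in infection with chlorhexidine presurgical preparations as opposed to povidone iodine". Section 12 words the goal differently again: "The primary aim of our study is to determine if UTI rates are similar between typical preoperative vaginal antiseptic cleaning solutions".

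Aims 2, 3 and 4 also hypothesise non-inferiority, and none has its own margin.

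**The concern.** A non-inferiority claim needs the data to exclude a difference as large as the margin. A test of no difference cannot do this: failing to reject may only mean that the trial is small. UTI yes/no is a categorical variable, so Section 13 assigns it the Wilcoxon-Mann-Whitney test. On 0/1 data that is nearly a chi-square test, so the name of the test is a minor matter. The problem is the null hypothesis and the absence of the 10%.

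Section 12 promises UTI rates by group, so a risk difference could be calculated afterwards. But the interval, its level and the criterion for success would then be chosen with the results in view. The differing statements of the goal (detecting no difference, similar rates, significance for non-inferiority) would leave room for more than one reading of the same data.

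**Working it through.** **Inputs.** From Section 5: 58 per group evaluable, up to 100 per group enrolled, 10%, alpha 0.05, power 80%, dropout 20%. Assumptions: 10% means 10 percentage points, and the 2-week UTI rate on povidone iodine (PI) is 5%, 10%, 20% or 33%. The documents give no 2-week rate; 33% is the 12-week figure in Section 2.

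**1. The plan's own figure.** With margin Δ = 0.10,

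n per group = (z₁₋α + z₀.₈₀)² × [p_CHG(1−p_CHG) + p_PI(1−p_PI)] / [Δ − (p_CHG − p_PI)]².

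- Equal rates of 5%, one-sided 0.05: 6.183 × 0.095 / 0.01 = 58.7, so 59. A rate of about 4.9% gives 58.
- Equal rates of 5%, one-sided 0.025: 7.849 × 0.095 / 0.01 = 74.6, so 75. A rate of about 3.8% gives 58.
- PI 20%, chlorhexidine (CHG) 11.2%, one-sided 0.025: 7.849 × 0.2595 / 0.188² = 57.6, so 58.
- Equal rates of 33%: 274 (one-sided 0.05) or 348 (one-sided 0.025).

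Several sets of assumptions give 58, so the sample size does not reveal which rule was intended.

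**2. Does the unstated level matter?** Take 6/58 (10.3%) in each arm. With equal counts the difference is 0 and the Newcombe upper limit is √[(u − p)² + (p − l)²], where l and u are the Wilson limits for one arm.

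- 90%: Wilson 0.0544 to 0.1878; √(0.0844² + 0.0490²) = 0.0976, or +9.8 points. Non-inferior.
- 95%: Wilson 0.0483 to 0.2079; √(0.1044² + 0.0552²) = 0.1181, or +11.8 points. Not shown.

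**3. Difference test against margin rule, 6 PI events of 58.** The Wilcoxon-Mann-Whitney test (tie-corrected, two-sided 0.05) is non-significant for every CHG count from 1 to 14, that is for observed differences from −8.6 to +13.8 points. The interval rule shows non-inferiority only for CHG counts up to 6 (90%) or 5 (95%). For example, 12/58 against 6/58 is 10.3 points worse, yet p = 0.126; the 90% interval is −0.8 to +21.4 points.

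**4. Long-run behaviour with CHG truly 10 points worse** (exact enumeration of two independent binomials):

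| PI rate | 5% | 10% | 20% | 33% |
|---|---|---|---|---|
| Difference test non-significant, 58 per group | 0.554 | 0.685 | 0.761 | 0.807 |
| Same, 100 per group | 0.317 | 0.485 | 0.631 | 0.693 |
| Non-inferior by 90% Newcombe rule, 58 per group | 0.053 | 0.051 | 0.052 | 0.056 |
| Same, 100 per group | 0.049 | 0.052 | 0.051 | 0.050 |

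The first two rows are error rates only if non-significance is read as non-inferiority.

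**5. Power of the margin rule.** The 19% and 44% lower odds are quoted in Section 2 for surgical site infection after abdominal preparation; applying them to UTI is an assumption.

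| PI rate | 5% | 10% | 20% | 33% |
|---|---|---|---|---|
| 90% interval, equal rates, 58 per group | 0.734 | 0.546 | 0.384 | 0.316 |
| 90%, CHG 19% lower odds, 58 | 0.824 | 0.693 | 0.572 | 0.523 |
| 90%, CHG 44% lower odds, 58 | 0.922 | 0.869 | 0.830 | 0.833 |
| 95% interval, equal rates, 58 | 0.555 | 0.398 | 0.270 | 0.211 |
| 95%, CHG 19% lower odds, 58 | 0.663 | 0.547 | 0.442 | 0.401 |
| 95%, CHG 44% lower odds, 58 | 0.807 | 0.762 | 0.728 | 0.744 |
| 90%, equal rates, 80 per group (100 less 20%) | 0.835 | 0.664 | 0.481 | 0.396 |
| 90%, equal rates, 100 per group | 0.908 | 0.745 | 0.550 | 0.455 |

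**The case against.** The ingredients of a margin test are arguably there. Section 5 ties 10% to a non-inferiority design with an alpha, Section 1 fixes the endpoint, window and direction, and Section 13 speaks of significance for a non-inferiority study. The sentence on tests is generic and does not name UTI, and the loose wording in Sections 5 and 12 may be lay phrasing rather than a success criterion. On this view the plan is under-specified, not wrong.

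Part of this stands. The probabilities of 0.55 to 0.81 are conditional on a reading that the plan does not state, and they are an illustration, not the plan's error rate. The 6/58 example also lies in a narrow window: with equal counts at 58 per group, the 90% and 95% rules disagree only for 4, 5 or 6 events per arm (3/58 passes both, 7/58 fails both), and 10/100 in each arm passes both. Power is better at 80 or 100 per group than at 58, although Section 5 allows enrolment to end once 58 per group have 2-week follow-up.

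None of this supplies the missing rule. The only tests named have the wrong null for the primary hypothesis, and a reader cannot recover the interval, level or criterion from the rest of the text.

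**Conclusion.** The concern holds. The analysis in Section 13 is wrong for the stated primary hypothesis, and this must be fixed before outcome data are analysed. That conclusion needs no assumption about rates. The sizes given do rest on the assumed PI rates and on reading 10% as absolute. Whether the stated 80% power is met depends on the PI rate, the CHG effect and the sidedness, none of which the documents give. Aims 2 to 4 have the same gap but are secondary. For Aim 4's 5-point scale, the Wilcoxon-Mann-Whitney test is a reasonable test of difference, but it is not a test of non-inferiority.

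**What to change.** In Section 13, replace the generic test sentence for the primary outcome with wording such as: *The primary analysis estimates the risk difference (CHG minus PI) in 2-week UTI with a prespecified score-type confidence interval (for example Newcombe). CHG is declared non-inferior only if the upper limit is below +10 percentage points. A non-significant test of difference is not evidence of non-inferiority.* Say also whether the conditional multivariate analysis is supportive only.

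In Section 5, confirm that the 10% is absolute, and state whether the one-sided level is 0.05 (90% interval) or 0.025 (95% interval). Restate power in Sections 5 and 13 for the chosen rule, with the assumed PI and CHG rates. Settle whether planning assumed equal rates or a reduction with CHG, since Sections 1 and 13 point different ways.

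For Aims 2 and 3, report the risk difference with its interval. For Aim 4, name one summary of the scale (for example the difference in mean score) and report it with its interval. Make no non-inferiority claim for these aims unless a margin is set before outcome data are analysed.

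The cost is wording, with no new data items. The downside to disclose is that the restated power at 58 per group may fall well short of 80%: with equal true rates and a 90% interval it runs from 73% at a PI rate of 5% down to 32% at 33%.
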